#### **8.4 Deaths, Serious Adverse Events, and Other Significant Adverse Events**

Treatment-emergent SAEs, TEAEs leading to study discontinuation, TEAEs resulting in death, treatment-emergent SAEs by relatedness, treatment-emergent SAEs leading to discontinuation, and treatment-emergent SAEs resulting in death will be summarized for all subjects in the safety population for each study phase. Summary tables will reflect a count and percentage of subjects experiencing at least 1 TEAE in each system organ class and preferred term within each AE subset (serious, leading to discontinuation, death). These summaries will be presented by treatment group and overall for each dose in the crossover phase and overall for each dose in the extension phase with percentages that

use the number of subjects in the safety population as the denominator. These tabular summaries will be sorted by descending frequency by system organ class and by preferred term in the MS1819 treatment group.

Adverse events leading to study discontinuation, AEs resulting in death, and SAEs will be presented in data listings for subjects in the safety population for each dose of the crossover phase and for each dose of the extension phase.

## **8.5 Clinical Laboratory Evaluation**

### **8.5.1 Crossover Phase**

Values at Screening and at 3 weeks post first dose, as described in Section 3, for laboratory parameters for hematology and clinical chemistry will be summarized by treatment group for the safety population using descriptive statistics. Values at Screening, Visit 3 (At Randomization), At First Dose, and at 3 Weeks Post First Dose, as described in Section 3, for laboratory parameters for urinalysis will be summarized by treatment group for the safety population using descriptive statistics.

Shift tables based on classification of values with respect to the reference range will be summarized for the safety population for critical clinical chemistry and hematology laboratory tests by treatment group. Critical clinical chemistry and hematology laboratory tests are listed in the appendix for Table Display Specifications.

Post-baseline elevations in alanine aminotransferase ( $\geq 3$  times the upper limit of normal [ULN]), aspartate aminotransferase ( $\geq 3$  times ULN), total bilirubin ( $\geq 1.5$  times ULN) will be summarized by treatment group at Screening and at 3 Weeks Post First Dose.

Hematology, clinical chemistry, hepatic monitoring, urinalysis, lipids, coagulation, and pregnancy results will be presented in data listings for subjects in the safety population.

### **8.5.2 Extension Phase**

Values for laboratory parameters for urinalysis, hematology and clinical chemistry will be summarized for the safety population using descriptive statistics.

Hematology, clinical chemistry, hepatic monitoring, urinalysis, lipids, coagulation, and pregnancy results will be presented in data listings for subjects in the safety population.

## **8.6 Vital Signs, Physical Findings, and Other Observations Related to Safety**

### **8.6.1 Vital Signs**

#### **8.6.1.1 Crossover Phase**

Values at Visit 3 (At Randomization), At First Dose, and at 3 Weeks Post First Dose, as described in Section 3, of systolic blood pressure, diastolic blood pressure, heart rate, respiratory rate, and temperature will be summarized by treatment group for the safety population using descriptive statistics.

Vital sign values will be presented in a data listing for all subjects in the safety population.

#### **8.6.1.2 Extension Phase**

Values of systolic blood pressure, diastolic blood pressure, heart rate, respiratory rate, and temperature will be summarized for the safety population using descriptive statistics for each dose of the extension phase.

Vital sign values will be presented in a data listing for all subjects in the safety population for each dose of the extension phase.

### **8.6.2 Physical Examinations**

A physical examination will be performed at study visits 3, 6, 9, and 10 of the crossover phase and at study visits 11, 13, 14, 16 and 17 of the extension phase. An indication of whether the examination was performed, date of the examination, and an indication of whether abnormal findings that were clinically significant were found will be collected. Because details of clinically significant abnormal findings will be entered on the medical history or AE form as appropriate, this data will be summarized with medical history and AEs, respectively.

### **8.6.3 Other Safety Measures**

#### **8.6.3.1 Prior and Concomitant Medications**

The prior and concomitant medications will be coded using the latest version of World Health Organization Drug Dictionary (WHODrug) Global Version (March 2020) to identify the drug class and preferred drug name.

Concomitant medications will include all medications that started on or after day of first dose of the study treatment in the first crossover period or that stopped on or after day of first dose of study treatment in the first crossover period. Prior medications will include

all medications that started and stopped prior to the day of first dose of the study treatment in the first crossover study period.

For the crossover period, concomitant medications will be categorized as occurring in study period 1 or study period 2. Concomitant medications that started or stopped on or after day of first dose of study treatment in period 1 and before the start of period 2 are attributed to period 1. Concomitant medications that started prior to the first dose of study treatment in period 1 and stopped on or after day of first dose of study treatment in period 1, or are ongoing, are attributed to period 1. Concomitant medications that started or stopped on or after day of first dose of study treatment in period 2 are attributed to period 2. Concomitant medications that started prior to the study and are stopped on or after day of first dose of study treatment in period 2, or are ongoing, are attributed to period 2.

For the extension phase, concomitant medications will be categorized into period (4.4 grams/day, 6.7 grams/day) using the same rules described above.

The number and percentage of subjects using prior and concomitant medications will be tabulated for each study period for the crossover phase and overall for the extension phase by Anatomical Therapeutic Chemical (ATC) level 1 term, ATC level 2 term, and preferred drug name for all subjects in the safety population. If a subject has more than 1 medication within an ATC level 1 term, the subject will be counted only once in that ATC level 1 term. Similarly, if a subject has more than 1 medication within an ATC level 2 term, the subject will be counted only once in that ATC level 2 term. If a subject has more than 1 medication that codes to the same preferred drug name, the subject will be counted only once for that preferred drug name. All percentages will use the number of subjects in the safety population as the denominator. The tabular summary will be sorted by descending frequency by ATC level 1 term, ATC level 2 term, and preferred drug name.

Prior and concomitant medications will be summarized separately for each dose of the crossover phase and for each dose of the extension phase.

Prior medications will be summarized overall (by planned treatment sequence for the crossover phase). Concomitant medications will be presented by actual treatment group and overall for the crossover phase and overall for the extension phase with percentages that use the number of subjects in the safety population as the denominator.

Prior and concomitant medication data will also be presented in a data listing for subjects in the safety population.

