- For a missing end day where the month and year are present, the end day will be set to the last day of the month, unless the month and year are the same as the month and year of the last contact date for the subject, in which case the end day will be set to that of the subject's last contact date.
- For a missing end day and month where the year is present, the end day and month will be set to the subject's last contact date, unless the year of the subject's last contact date is greater than the end year, in which case the end day and month will be set to December 31st.

To categorize events with partial dates into their associated treatment periods, the imputation rules above will be defined relative to the first dose of the treatment period of interest separately (first treatment period of crossover, second treatment period of

crossover, 4.4 grams/day dose stage of the extension phase, 6.7 grams/day dose stage of the extension phase), as applicable. Thus, in the aforementioned rules, ‘study treatment’ refers to the treatment in the specified treatment period. Per the imputation rules, events with partial dates may require multiple imputed start dates to account for each treatment period. For example, an event with missing start day where the start month is the same as the treatment start month for both study treatments of the crossover period will have the start date imputed to both the treatment start date of the first crossover study period and the treatment start date of the second crossover study period.

Partial and completely missing dates will be imputed for the purposes of classifying concomitant medications as follows:

- Partial dates will be imputed following the same algorithm as above for TEAEs.
- For a missing start date (i.e., day, month, and year are missing), the start date will be set to the date of first dose of study treatment for each period (first treatment period of crossover, second treatment period of crossover, first dose period of the extension phase, second dose period of the extension phase), as applicable, unless the stop date is prior the date of first dose of study treatment for a given period, in which case the start date will be set to the stop date.
- For a missing stop date (i.e., day, month, and year are missing), the medication will be treated as ongoing.

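### SAP 8.6.3.1 gives crossover period 2 no end and medications no follow-up category, so drugs started after period 2 are counted under the period-2 treatment; its ongoing clause is also ambiguous

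*SAP*

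**What the plan says.** SAP 8.6.3.1 assigns medications to crossover periods in four sentences.

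- Period 1, by date: drugs that "started or stopped on or after day of first dose of study treatment in period 1 and before the start of period 2". This rule has both a lower and an upper limit.
- Period 1, carry-in: "started prior to the first dose of study treatment in period 1 and stopped on or after day of first dose of study" (the sentence goes on to specify the period-1 dose). Ongoing drugs also qualify.
- Period 2, by date: "Concomitant medications that started or stopped on or after day of first dose of study treatment in period 2 are attributed to period 2". This rule has a lower limit only.
- Period 2, carry-in: drugs that "started prior to the study and are stopped on or after day of first dose of study treatment in period 2, or are ongoing".

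The period then decides the treatment column: "Concomitant medications will be presented by actual treatment group and overall for the crossover phase". For the extension: "For the extension phase, concomitant medications will be categorized into period (4.4 grams/day, 6.7 grams/day) using the same rules described above". SAP 8.1 adds that when the stop date is wholly missing, "the medication will be treated as ongoing".

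SAP 8.3 handles adverse events differently. It closes period 2 at the end of period-2 treatment, classes later events as follow-up, separates that follow-up from the extension, and has a tie-break for untimed events on the crossover date.

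**The concern.** SAP 8.1 lists concomitant medications among the safety measures summarized by actual treatment, so that MS1819 and PERT can be compared within patients. That comparison is only as good as the allocation of each drug to a period.

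Medication data continue after period 2. Protocol 8.3.3 records changes at Visit 10, about two weeks after the last dose, and by then Protocol 8.3 (Visit 9) has returned every patient to pre-study PERT. With no end to period 2, a drug begun in those two weeks goes into the period-2 column. An adverse event in the same two weeks is classed as follow-up, so an event and the drug given for it can appear under different headings.

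SAP section 1 gives the SAP primacy over the protocol, so these sentences are the ones a programmer will implement.

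**Working it through.** The plan gives no figure to reproduce. The check applies the four sentences literally and compares the result with the periods in which the drug was actually in use.

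**Inputs.** Start: before consent, screening, period 1 (P1), period 2 (P2), follow-up, extension. Stop: P1, P2, follow-up, extension, or none (ongoing). Patterns that stop before the first dose are prior medications and are left out. The number of patterns by start is 5 + 5 + 5 + 4 + 3 + 2 = 24.

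**True membership.** A drug belongs to a period if it started no later than the end of that period and either stopped no earlier than its first dose or is ongoing.

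**Readings.** *Tied*: the ongoing clause applies only to drugs that meet the start condition in the same sentence. *Stand-alone*: any ongoing drug qualifies. The start of the study, named in the period-2 carry-in sentence, was taken as consent or as first dose. All patterns that are wrong on at least one reading:

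| Start | Stop | True | Tied | Stand-alone |
|---|---|---|---|---|
| Screening | none | P1, P2 | P1 only, if the study starts at consent; otherwise correct | correct |
| P1 | none | P1, P2 | P1 only | correct |
| P2 | none | P2 | correct | P1, P2 |
| Follow-up | follow-up | neither | P2 | P2 |
| Follow-up | extension | neither | P2 | P2 |
| Follow-up | none | neither | P2 | P1, P2 |
| Extension | extension | neither | P2 | P2 |
| Extension | none | neither | P2 | P1, P2 |

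**Totals.**
- Tied, study starts at first dose: 1 + 5 = 6 of 24.
- Tied, study starts at consent: 2 + 5 = 7 of 24.
- Stand-alone, either start: 1 + 5 = 6 of 24.

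The five follow-up and extension rows are wrong on every reading. If the two extension-start rows are set aside as outside the intended scope, 22 patterns remain, with 6 - 2 = 4, 7 - 2 = 5 and 6 - 2 = 4 errors.

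**Where the error arises.** The open-ended stop condition does no harm: a drug begun in or before period 2 and stopped later was in use during period 2. The open-ended start condition causes all five rows. In the first two rows of the table, the by-date rule cannot rescue the drug because there is no stop date to test.

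**Which column is wrong.**
- PERT then MS1819: a follow-up drug is counted under MS1819 while the patient takes PERT.
- MS1819 then PERT: a follow-up drug is counted under PERT, which the patient is still taking. The period is wrong but the treatment label is right.

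**Overlap rule.** The rule proposed under the fix gives 0 of 24 mismatches. The grid has no same-day cases, so this does not test the crossover date itself.

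**The case against.** The strongest case against is that the consequence is small and the intent is mostly recoverable. The tables are descriptive, with no test, and SAP 8.6.3.1 also lists every medication. Follow-up lasts about two weeks, and the treatment label is wrong in only one of the two sequence orders. Drugs begun and stopped within period 1, begun in period 1 and stopped in period 2, or begun and stopped within period 2 are placed correctly, which covers ordinary short antibiotic courses. All of this stands and limits the size of the point.

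Four stronger readings are tempting, but the documents do not support them.

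- *A reader might infer that period-2 use is generally dropped.* It is not. Only drugs with no stop date are in question, and only on the tied reading.
- *A reader might infer that every extension participant's drugs contaminate the crossover tables.* The period rules open by limiting themselves to the crossover, a separate sentence covers the extension, and the phases are summarized separately. What remains is that no sentence explicitly removes extension-started drugs.
- *A reader might infer that a pre-study ongoing drug is counted under period 2 for a patient who never entered it.* The carry-in sentence does not exclude this, but the tables use actual treatment and such a patient has no period-2 treatment. The claim is doubtful and was not tested.
- *A reader might infer that the drugs most telling about tolerability are the ones misplaced.* Most new use during treatment is placed correctly. Acid suppressants are a poor example, because Protocol 7.5 requires a stable dose throughout.

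**Conclusion.** The point holds as a minor one: the rule is wrong as written. On every reading tested, a drug first started after the last period-2 dose is counted in period 2, and in the PERT-then-MS1819 sequence it appears under the wrong treatment. The ongoing clause needs a decision, because each reading produces a different error. The same gaps pass to the extension, where the last stage is likewise open-ended.

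The size is 6 or 7 of 24 logical patterns, or 4 or 5 of 22 without extension starts. The patterns are equally weighted, so these figures say nothing about how many patients or records will be affected; the documents give no basis for that. The result assumes the sentences are programmed literally. CFA, the other efficacy summaries and the listings are unaffected.

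**What to change.** Replace the four sentences with one overlap rule in line with SAP 8.3:

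1. A medication belongs to a period the patient entered if it started on or before the end of that period's treatment and either stopped on or after the first dose of that period or is ongoing.
2. A medication started on the crossover date without a recorded time goes to one period by a stated tie-break, for example the one SAP 8.3 uses for adverse events (period 1). This is needed because Protocol 7.1 has no washout and Protocol 8.3 switches patients at once; without it, such a drug could count in both periods.
3. A medication started after the last crossover dose and before any extension dosing is classed as crossover follow-up.
4. A medication started in the extension is counted only in the extension.
5. The same rule applies to each extension stage.

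The cost is SAP wording and simpler programming. No new data are needed, because start dates, stop dates and dosing dates are already used in the SAP.

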## **9. EFFICACY EVALUATION**

### **9.1 Overview of Efficacy Analysis Issues**

#### **9.1.1 Handling of Dropouts or Missing Data**

Missing data will not be replaced.

#### **9.1.2 Assessment Time Windows**

Rules for assessment time windows are addressed in Section [9.2](#) for each efficacy endpoint.

## 9.2 Analysis Methods

### 9.2.1 Crossover Phase: Primary Efficacy Analyses

The primary efficacy endpoint is the CFA assessed at the end of each 3-week treatment period (Visit 6 or Visit 9). CFA is evaluated by the 72-hour marker-to-marker stool sample collection (1 measure at Visit 6 and 1 at Visit 9) and standardized high-fat diet during each supervised confinement. Coefficient of fat absorption represents the percentage of fat absorbed from the diet by the subject and is calculated from the results of the quantitative fecal fat measurement in conjunction with the dietary fat intake.

CFA will be calculated by using 2 data points:

- Fat consumption in grams/24h (converted from fat consumption in grams/72h as provided by the qualified dietician at each site).
- Fat excretion in grams/24h as provided by the central laboratory.

CFA will be calculated as follows:

$$\frac{(\text{Grams/24h of fat consumed} - \text{Grams/24h of fat excreted}) \times 100}{\text{Grams/24h of fat consumed}}$$

The primary efficacy endpoint analysis of the crossover phase will use the mITT population and be analyzed as randomized for each dose. For the summary of CFA, if a subject switches study treatments (i.e. MS1819 to PERT or PERT to MS1819) during the confinement period, prior to the end of the stool collection, then the CFA value during that confinement period will be excluded from the summary.

CFA at the end of the first period (Visit 6) and CFA at the end of the second period (Visit 9) will be summarized by treatment group for each dose using descriptive statistics.

Fat consumed (g/24h), fat excreted (g/24h), and CFA (%) will be listed by visit for all subjects in the mITT population for each dose.

Details of each supervised confinement, including controlled diet and marker-to-marker stool collection, will be listed for all subjects in the mITT population for each dose.

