### **Primary Analysis:**

The primary analysis of the primary endpoint will be a comparison of the mean CFAs from the MS1819 treatment vs the PERT treatment, using descriptive statistics. This analysis will be conducted for each of the two MS1819 doses.

An exploratory analysis of non-inferiority between the MS1819 and PERT groups will be conducted. The treatment effect, along with the 95% confidence interval of the difference in CFA (MS1819 minus porcine PERT), will be estimated. Non-inferiority will be claimed if

the lower bound of the 95% confidence interval is greater than -15%, where 15% is the non-inferiority margin.

Subgroup analyses: Analyses of CFA considering the same approach used for the primary analysis will be performed in the following subgroups:

- by CFA level while receiving porcine PERT (<80% vs ≥80%). An analysis will be done in the subgroup of Patients with CFA below 80% while receiving porcine PERT, as well as in the subgroup of patients with CFA of 80% or greater while receiving porcine PERT.
- by those receiving versus not receiving gastric acid suppression.

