## **1. PURPOSE OF THE ANALYSES**

The statistical analysis plan (SAP) is being developed after review of the AzurRx BioPharma, Inc. (AzurRx), protocol number AZ-CF2002, but before any analyses of the data. The SAP contains detailed information to aid in the implementation of the statistical analyses and reporting of the study data for use in the clinical study report (CSR). This SAP is being written with due consideration of the recommendations outlined in the most recent International Conference on Harmonisation (ICH) E9 Guideline entitled Guidance for Industry: Statistical Principles for Clinical Trials and the most recent ICH E3 Guideline, entitled Guidance for Industry: Structure and Content of Clinical Study Reports.

This SAP describes the analysis sets that will be analyzed, the subject characteristics parameters, the efficacy parameters, and the safety parameters that will be evaluated. The details of the specific statistical methods that will be used will be provided in this SAP. If differences occur between analyses described in the SAP and the current protocol, those found in this SAP will assume primacy. If additional analyses are required to supplement the planned analyses described in this SAP, they may be completed and will be identified in the CSR. Table and listing specifications are provided in a separate document.

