### 3. GENERAL ANALYSIS AND REPORTING CONVENTIONS

The following is a list of general analysis and reporting conventions to be applied for this study.

Categorical variables will be summarized using counts (n) and percentages (%) and will be presented in the form “n (xx.x).” If a count is 0, 0% will be shown for the percentage. To ensure completeness, summaries for categorical and discrete variables will include all categories, even if no subjects had a response in a particular category.

Continuous variables will be summarized using mean, SD, minimum, maximum, median and number of subjects. The 25th and 75th percentiles will be provided for distributions that are known to be skewed. The mean, median, 25th percentile, 75th percentile, and confidence intervals (CI) will be reported to 1 more level of precision than the original observations, and the SD will be reported to 2 more levels of precision than the original observations. The minimum and maximum will be the same precision as the original data.

When p-values are provided, they will be rounded to 3 decimal places; p-values that round to “0.000” will be presented as “<0.001.” Unless otherwise stated, all statistical tests of treatment effects will be conducted at a 2-sided alpha level of 0.05.

All analysis will be performed using SAS® System version 9.3 or later.

Dates in listings will be displayed as yyyy-mm-dd (e.g., 2015-01-24).

Separate displays will be produced for each crossover phase dose (2240 mg/day, 4480 mg/day) and each extension phase dose (4.4 grams/day, 6.7 grams/day), unless otherwise stated.

For the crossover phase, in order to present summaries by treatment group regardless of sequence, the following parameters will be summarized as described below: safety laboratory, vital signs, signs and symptoms of malabsorption, weight, BMI, and serum liposoluble vitamins A, D, E, and K. These endpoints will be summarized relative to the time of first dose on a given study treatment. All post-randomization measurements will be relative to the time of the first dose. For example, in the MS1819 treatment column, the measurement at first dose will be Visit 3 if a subject is randomized to the MS1819-PERT sequence, and Visit 6 if a subject is randomized to the PERT-MS1819 sequence.

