### 9.2.2.1 Coefficient of Nitrogen Absorption

CNA at the end of each treatment period (Visit 6, Visit 9) will be analyzed. CNA will be expressed as the percentage of nitrogen (protein) absorbed from the subject's diet.

CNA will be calculated using 2 data points:

- Nitrogen consumption in grams/24h (converted from fat consumption in grams/72h as provided by the qualified dietician at each site)
- Nitrogen excretion in grams/24h as provided by the central laboratory

CNA will be calculated as follows:

$$\frac{(\text{Grams/24h of nitrogen consumed} - \text{Grams/24h of nitrogen excreted}) \times 100}{\text{Grams/24h of nitrogen consumed}}$$

CNA at the end of the first period (Visit 6) and CNA at the end of the second period (Visit 9) will be summarized by treatment group for each dose using descriptive statistics. For the summary of CNA, if a subject switches study treatments (i.e. MS1819 to PERT or PERT to MS1819) during the confinement period, prior to the end of the stool collection, then the CNA value during that confinement period will be excluded from the summary. Missing CNA values will not be imputed.

A secondary (supportive) descriptive summary of CNA will be provided using the per-protocol population, according to randomized treatment group.

Nitrogen consumed (g/24h), nitrogen excreted (g/24h), and CNA (%) will be listed by visit for all subjects in the mITT population.

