## **11. CHANGES TO THE ANALYSES PLANNED IN THE PROTOCOL**

Section 10.7.1 of the protocol states that an exploratory analysis of non-inferiority between the MS1819 and PERT groups will be conducted for CFA (MS1819 minus porcine PERT) with a non-inferiority margin of 15%. Section 10.7.2 of the protocol states that CNA will be analyzed in the same manner as CFA. The non-inferiority analyses for CFA and CNA will not be conducted.

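### The SAP removes the MS1819-minus-PERT difference in CFA with its 95% CI and puts no treatment contrast or precision in its place

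*SAP*

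**What the plan says.** Protocol 10.7.1 and the synopsis make the primary analysis a descriptive comparison of mean CFA for each MS1819 dose. They add an exploratory non-inferiority analysis, which contains this commitment: "The treatment effect, along with the 95% confidence interval of the difference in CFA (MS1819 minus porcine PERT), will be estimated". The margin is 15 points. Protocol 10.7.2 has CNA analysed the same way.

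SAP section 11 then states: "The non-inferiority analyses for CFA and CNA will not be conducted". It gives no reason and names no replacement. SAP section 1 sets the precedence: "If differences occur between analyses described in the SAP and the current protocol, those found in this SAP will assume primacy".

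What remains is SAP 9.2.1 for CFA ("CFA at the end of the second period (Visit 9) will be summarized by treatment group for each dose using descriptive statistics", with the same for Visit 6) and SAP 9.2.2.1 for CNA ("CNA at the end of the second period (Visit 9) will be summarized by treatment group for each dose using descriptive statistics"). SAP section 3 defines those statistics: "Continuous variables will be summarized using mean, SD, minimum, maximum, median and number of subjects", with quartiles for skewed variables. The per-protocol and subgroup sections repeat the same summary.

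The only SAP sentence about intervals is a rounding rule in section 3: "confidence intervals (CI) will be reported to 1 more level of precision than the original observations". SAP section 12 lists a crossover-trials textbook and a small-sample mixed-model paper, but no methods text uses either.

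**The concern.** A 2x2 crossover is run so that each patient is compared with himself or herself. Summaries by treatment column, or by treatment and visit, do not report that comparison. Their SDs do not carry the within-patient correlation, so the precision of the contrast cannot be worked out from them.

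The two columns may also hold partly different patients. The modified intent-to-treat (mITT) set requires only one valid CFA, missing values are not replaced, and a value is excluded if the patient switches treatment during confinement. In OPTION, the prior trial, five patients left during MS1819 and three during PERT, so the loss need not be even.

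If a difference is reported after all, three choices will be made with the data in view: the contrast method, whether to adjust for period, and whether to restrict to complete pairs.

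**Working it through.** **Text check.** Setting the sections side by side, the difference and its CI appear only within the protocol's non-inferiority paragraph. SAP 11 cancels that analysis, no other SAP section plans the estimate, and SAP 1 gives the SAP precedence. No contrast survives in the SAP text.

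**The plan's own figure.** Protocol 10.2 and SAP 2.6 give 15 patients per dose as enough for point estimates. No SD, precision target or power is stated, so this number cannot be reproduced.

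**Inputs.**
- OPTION CFA (Protocol 5.6.3): MS1819 mean 56, range 7 to 92 (width 85); PERT mean 86, range 57 to 97 (width 40).
- The documents give no SDs. The simulated expected range of a normal sample is 4.14 SD at n = 32 and 4.24 SD at n = 36. Using 4.15: 85/4.15 = 20.5 and 40/4.15 = 9.6. The PERT range is skewed, so SD pairs from 16/7 to 25/12 are also shown.
- Within-patient correlation (rho): assumed 0, 0.3 or 0.6.
- Pairs per dose: 15 (7+8 by sequence) or 14 (7+7).

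**Formulas.** The SD of the paired difference is sqrt(20.5² + 9.6² − 2·rho·20.5·9.6), which is 22.6, 19.9 or 16.6. The period-adjusted SE is SD·sqrt(0.25·(1/n1 + 1/n2)). The half-width is t(0.975, n1+n2−2)·SE.

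| Pairs | t | SE at rho 0 / 0.3 / 0.6 | 95% half-width |
|---|---|---|---|
| 15 (7+8) | 2.160 | 5.86 / 5.14 / 4.30 | 12.7 / 11.1 / 9.3 |
| 14 (7+7) | 2.179 | 6.05 / 5.31 / 4.44 | 13.2 / 11.6 / 9.7 |

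Sensitivity to the assumed SDs, half-widths at rho 0 / 0.3 / 0.6:

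| SDs (MS1819/PERT) | 15 pairs | 14 pairs |
|---|---|---|
| 16/7 | 9.8 / 8.6 / 7.3 | 10.2 / 9.0 / 7.6 |
| 25/12 | 15.5 / 13.6 / 11.3 | 16.1 / 14.1 / 11.8 |

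**Illustration.** At rho 0.3 with 15 pairs, an observed difference of −15 has an interval of −15 ± 11.1, or −26.1 to −3.9.

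**What the planned summaries would allow.** Treating the columns as independent with n = 15, SE = sqrt(20.5²/15 + 9.6²/15) = 5.84. Welch df is 19.9, t is 2.087 and the half-width is 12.2. Against the paired values this is 0.5 points too narrow at rho 0 and 2.9 too wide at rho 0.6. The summaries do not show which case applies.

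**Incomplete pairs.** Protocol 7.3.1 plans 36 enrolled, so 36/2 = 18 per dose. At its 20% withdrawal rate, 18 × 0.8 = 14.4 complete both periods and 3.6 do not. In OPTION, 32 completers plus one who left after both periods is 33 of 41: 18 × 33/41 = 14.5 complete and 18 × 8/41 = 3.5 incomplete. About 3 to 4 of 18 would contribute to at most one column.

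**The case against.** **The primary analysis has not changed.** The protocol called it descriptive rather than inferential, sized the trial only for point estimates, and labelled the lost item exploratory. SAP 11 declares the change openly. All of this stands and keeps the point below a critical fault. It does not supply a contrast. An interval offered as estimation is compatible with a descriptive analysis, and the protocol planned the two together.

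**SAP 11 cancels the non-inferiority analyses without expressly withdrawing the estimate.** That is fair on the wording. But no SAP section plans the estimate, so at best its status is unclear, and one sentence would settle it.

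**The table specifications, a separate attachment, might show a difference or an interval.** This cannot be excluded. The conclusion is limited to the SAP text.

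**The data will exist.** The Visit 6 and Visit 9 sentence can be read as treatment-by-period summaries, which give a period-adjusted point difference. Listings allow pairing later: "CFA (%) will be listed by visit for all subjects in the mITT population for each dose". The SAP also fixes the analysis set, the validity rule and the handling of missing values. What stays open is the contrast method, the period adjustment and the choice of pairs.

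**The numbers are assumption-driven and the −15 example is chosen at the margin.** OPTION's observed gap, with the immediate-release capsule, was 56 − 86 = −30. At a half-width of 11.1 that gives about −41 to −19, clear of −15. The practical gap between paired and column-based intervals is also only about 3 points at most for the correlations shown. Both remarks are correct. They limit the consequence, but the reader still needs the interval to know which situation applies.

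**Period adjustment goes beyond the protocol.** It does. It is the standard analysis for this design and costs one degree of freedom.

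**Conclusion.** The point holds and should be fixed. As written, the SAP text yields no within-patient treatment effect and no precision for the primary comparison of a crossover trial. The unreported uncertainty per dose is roughly ±9 to ±13 CFA points at the central SDs, and ±7.3 to ±16.1 over all the SDs, correlations and pair counts shown. Those figures rest on SDs back-calculated from ranges under normality and on assumed correlations. The textual conclusion does not depend on them. What is missing is a pre-specified contrast and its interval, not the data. Dropping the non-inferiority claim is not itself at fault.

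**What to change.** In SAP 9.2.1, keep the descriptive summaries and make no non-inferiority claim. Add for each dose:

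1. The within-patient CFA difference (MS1819 minus PERT) with a period-adjusted 95% CI: the average of the two sequence-mean differences, with t on n1+n2−2 df, labelled estimation only.
2. The number of complete pairs.

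Do the same for CNA in SAP 9.2.2.1. Beside the primary table, list the number of patients who started MS1819 without a valid MS1819 CFA, with reasons. SAP 5.1 already counts period withdrawals with reasons, so the addition is mainly invalid or excluded collections. No imputation is needed. Record all this in SAP 11 as what replaces the dropped analysis.

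A separate, smaller repair: Protocol 7.3.4 places withdrawn patients who received study product in the mITT efficacy analysis, whereas the mITT definition requires a valid CFA. The two must be reconciled.

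Cost: SAP wording and one extra table per endpoint, from data already collected. The 7.3.4 point also needs a protocol clarification or an entry in SAP 11. The downside is a wide interval with about 14 to 15 pairs per dose, which must not be read as a non-inferiority test.
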